#### **6.1.2           Adverse Event Severity**

##### **Intensity of AEs**

The investigator will use the following definitions to rate the severity of each adverse event:

**Mild**

The adverse event is transient and easily tolerated by the subject.

Moderate	The adverse event causes the subject discomfort and interrupts the subject's usual activities.
Severe	The adverse event causes considerable interference with the subject's usual activities and may be incapacitating or life-threatening.

### **6.1.3 Relationship to Study Drug**

The investigator will use the following definitions to assess the relationship of the adverse event to the use of study drug:

Reasonable Possibility	After consideration of factors including timing of the event, biologic plausibility, clinical judgment, and potential alternative causes, there is sufficient evidence (information) to suggest a causal relationship.
No Reasonable Possibility	After consideration of factors including timing of the event, biologic plausibility, clinical judgment, and potential alternative causes, there is insufficient evidence (information) to suggest a causal relationship.

For causality assessments, events assessed as having a reasonable possibility of being related to the study drug will be considered "associated." Events assessed as having no reasonable possibility of being related to study drug will be considered "not associated." In addition, when the investigator has not reported a causality or deemed it not assessable, AbbVie will consider the event associated.

If an investigator's opinion of no reasonable possibility of being related to study drug is given, an Other cause of event must be provided by the investigator for the serious adverse event.

[figure not shown]
### **6.1.4 Adverse Event Collection Period**

All adverse events reported from the time of study drug administration until 15 weeks following discontinuation of risankizumab and 7 weeks following discontinuation of FUMADERM® (provided as study medication) administration have elapsed will be

collected, whether solicited or spontaneously reported by the subject. In addition, serious adverse events and protocol-related non-serious adverse events will be collected from the time the subject signed the study-specific informed consent.

Adverse event information will be collected as shown in [Figure 3](#).

**Figure 3. Adverse Event Collection**

### 6.1.5 Adverse Event Reporting

In the event of a serious adverse event, whether associated with study drug or not, the Investigator will notify Clinical Pharmacovigilance within 24 hours of the site being made aware of the serious adverse event by entering the serious adverse event data into the electronic data capture (EDC) system. Serious adverse events that occur prior to the site having access to the RAVE® system, or if RAVE is not operable, should be documented on the SAE Non-CRF forms and emailed (preferred route) or faxed to Clinical Pharmacovigilance within 24 hours of the site being made aware of the serious adverse event.

**24-hour AbbVie Medical Escalation**  
**Phone Hotline:** [REDACTED]

The sponsor will be responsible for Suspected Unexpected Serious Adverse Reactions (SUSAR) reporting for the Investigational Medicinal Product (IMP) in accordance with Directive 2001/20/EC. The reference document used for SUSAR reporting in the EU countries will be the most current version of the Investigator's Brochure for risankizumab and the Summary of Product Characteristics for FUMADERM® INITIAL and FUMADERM®.

### **6.1.6      Pregnancy**

Pregnancy in a study subject must be reported to AbbVie within 1 working day of the site becoming aware of the pregnancy. Subjects who become pregnant during the study must be discontinued (Section 5.4.1).

Information regarding a pregnancy occurrence in a study subject and the outcome of the pregnancy will be collected.

Pregnancy in a study subject is not considered an adverse event. The medical outcome for either mother or infant, meeting any serious criteria including an elective or spontaneous abortion, is considered a serious adverse event and must be reported to AbbVie within 24 hours of the site becoming aware of the event.

## **6.2           Product Complaint**

### **6.2.1       Definition**

A Product Complaint is any Complaint (see Section 6.0 for the definition) related to the biologic or drug component of the product or to the medical device component(s).

For a product this may include, but is not limited to, damaged/broken product or packaging, product appearance whose color/markings do not match the labeling, labeling discrepancies/inadequacies in the labeling/instructions (example: printing illegible), missing components/product, device not working properly, or packaging issues.

For medical devices, a product complaint also includes all deaths of a patient using the device, any illness, injury, or adverse event in the proximity of the device, an adverse event that could be a result of using the device, any event needing medical or surgical intervention including hospitalization while using the device and use errors.

Any information available to help in the determination of causality by the device to the events outlined directly above should be captured.

#### **6.2.2 Reporting**

Product Complaints concerning the investigational product and/or device must be reported to the Sponsor within 24 hours of the study site's knowledge of the event via the Product Complaint form. Product Complaints occurring during the study will be followed-up to a satisfactory conclusion. All follow-up information is to be reported to the Sponsor (or an authorized representative) and documented in source as required by the Sponsor. Product Complaints associated with adverse events will be reported in the study summary. All other complaints will be monitored on an ongoing basis.

Product Complaints may require return of the product with the alleged complaint condition (syringe). In instances where a return is requested, every effort should be made by the investigator to return the product within 30 days. If returns cannot be accommodated within 30 days, the site will need to provide justification and an estimated date of return.

The description of the complaint is important for AbbVie in order to enable AbbVie to investigate and determine if any corrective actions are required.

### **7.0 Protocol Deviations**

AbbVie does not allow intentional/prospective deviations from the protocol unless when necessary to eliminate an immediate hazard to study subjects. The principal investigator is responsible for complying with all protocol requirements, and applicable global and local laws regarding protocol deviations. If a protocol deviation occurs (or is identified)

---

after a subject has been enrolled, the principal investigator is responsible for notifying Independent Ethics Committee (IEC)/Independent Review Board (IRB) regulatory authorities (as applicable), and the following AbbVie Clinical Monitor(s):

Primary Contact:

Alternate Contact:

Such contact must be made as soon as possible to permit a review by AbbVie to determine the impact of the deviation on the subject and/or the study.

## **8.0                    Statistical Methods and Determination of Sample Size**

The specification described here is that envisaged at the time of planning the trial. Should new evidence come to light as a result of running other trials before this trial is analyzed, or should new methods of analysis become available in the statistical literature, or should the trial be affected by unforeseen circumstances, it may be necessary to modify the analysis strategy.

The analysis strategy described below will be supplemented by a detailed statistical analysis plan (SAP), which will be completed prior to database lock.

**8.1 Statistical and Analytical Plans****8.1.1 Analysis Populations**

The intent-to-treat (ITT) population consists of all subjects who were randomized. The safety population consists of all subjects who were randomized and received at least one dose of study drug.

In order to evaluate the impact of major protocol deviations on the results of the trial, additional sensitivity analyses may be performed on the per-protocol population, which excludes subjects with major protocol deviations from the ITT population. If it is decided that this analysis should be performed, the criteria for exclusion of subjects from the protocol analysis will be fully defined and documented in the final SAP and before the database lock.

**8.1.2 Planned Methods of Statistical Analysis**

All statistical tests will be two-tailed. The statistical tests for the primary endpoint will be performed at the significance level 0.05. All  $P$  values will be rounded to 3 decimal places. Descriptive statistics will be provided. These include the number of observations, mean, standard deviation, minimum, median, quartiles and maximum for continuous variables, and counts and percentages for discrete variables. The analyses will be performed using SAS® (SAS Institute Inc., Cary, NC, USA).

**8.1.3 Demographic and Baseline Characteristics**

Demographics and Baseline characteristics of the study subjects will be summarized for each treatment arm using descriptive statistics. Statistical tests will be performed to assess the comparability of the treatment arms. Continuous variables will be analyzed using one-way analysis of variance (ANOVA), and discrete variables will be analyzed using Chi squared test or Fisher's exact test as appropriate.

**8.1.4 Analysis of Efficacy**

All efficacy analyses will be performed in the ITT population.

The primary efficacy endpoint (PASI90 at Week 24) will be analyzed using a two-sided Cochran-Mantel Haenszel test stratified by prior phototherapy at level of significance 5%. Missing data will be imputed using non-responder imputation, i.e., a subject with missing PASI90 at Week 24 will be considered a non-responder in the primary analysis. Further sensitivity analyses for the primary endpoint may be specified in the SAP prior to database lock.

For the analysis of categorical secondary endpoints, the same statistical test as for the primary endpoint will be performed, missing data will be imputed using non-responder imputation. For the analysis of continuous secondary endpoints, two-sided two-way ANOVA with treatment and prior phototherapy as factors will be imputed using last observation carried forward (LOCF).

The order of the secondary endpoints does not reflect a ranking and secondary endpoints will not be used for confirmatory interpretation, thus no adjustment for multiplicity will be done.

Further details regarding the statistical analysis will be specified in the SAP.

### **8.1.5 Analysis of Safety**

All safety analyses will be performed in the safety population.

Treatment-emergent adverse events are defined as events with an onset date on or after the first dose of study drug until 15 weeks (105 days) following the last dose of risankizumab or 1 week (7 days) after the last dose of FUMADERM® provided as study medication or until rollover into the extension study. In a sensitivity analysis, adverse events with an onset date until 7 weeks (49 days) after the last dose of FUMADERM® provided as study medication or until rollover into the extension study will be included.

SAEs and protocol-related non-serious AEs with onset after informed consent but before the first study drug administration will be considered as pretreatment events and reported separately.

Adverse events will be tabulated by system organ class and preferred term, whereby the most current implemented MedDRA dictionary will be used. Also, summaries by severity and relationship to study drug will be done. Certain adverse events, like serious or severe, leading to discontinuation, will be listed and described in detail. Adverse events of interest for treatment with biologics will be defined in the statistical analysis plan and analyzed separately.

Adverse events will be summarized by frequency and percentage and presented by treatment group, statistical comparisons will be performed using Fisher's exact test.

Other safety variables like laboratory data and vital signs will also be described by descriptive statistics for each treatment group. Treatment comparisons will be performed by one way ANOVA. In addition, shift tables and listings will be provided for abnormal values, whereby the normal range of the analyzing laboratory will be used.

#### **8.1.6                   Interim Analysis**

No interim analysis will be done for this study.

#### **8.1.7                   Pharmacokinetic and Exposure-Response Analysis**

Individual risankizumab serum concentrations will be tabulated and summarized with appropriate statistical methods. In addition, ADA titers will be tabulated for each subject at the respective study visits. The number and percentage of subjects with ADA will be calculated.

Additional analyses with combining pharmacokinetic and ADA data from this study and other studies may be conducted if appropriate; this may include exploratory analyses of the effect of ADA on risankizumab pharmacokinetics and efficacy as well as the relationships between exposure and clinical observations (efficacy or safety variables of interest). Such analyses, if conducted, may be summarized in a separate report rather than in the clinical study report for this study.

## **8.2 Determination of Sample Size**

Using a two-sided Chi squared test at level of significance 5%, the sample size of 110 (2 × 55) subjects will provide 94% power assuming response rates of the primary endpoint (PASI90 at Week 24) of 70% for risankizumab and 35% for FUMADERM®.

These assumptions are in line with what has been observed in recent studies for Risankizumab (63/83 (75.9%) at Week 24) and FUMADERM® 61/273 (22.3%) of the subjects achieved PASI 90 at Week 16 in the FUMADERM® arm in the BRIDGE trial.

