## **8.3 Randomization Methods**

An IVR/IWR system will be used to determine the randomization of subjects. Detailed instructions for using the IVR/IWR system will be provided to the site personnel.

The randomization schedule will be prepared by the statistics department of AbbVie. Subjects who are eligible based on inclusion and exclusion criteria and have had all pre-randomization procedures performed will be randomized in a 1:1 ratio to receive risankizumab or FUMADERM® stratified by prior phototherapy, with a maximum of 20% of subjects with prior phototherapy. Randomization will not be stratified by center due to the limited number of subjects per center. Randomization will be done using an adequate block size.

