**Figure 1. Study Design Schematic**

**4.3 Sample Size**

Using a two-sided Chi squared test at level of significance 5%, the sample size of 110 (2 × 55) subjects will provide 94% power assuming response rates of the primary endpoint (PASI 90 at Week 24) of 70% for risankizumab and 35% for FUMADERM®.

These assumptions are in line with what has been observed in recent studies for risankizumab (63/83 (75.9%) at Week 24) and FUMADERM® 61/273 (22.3%) of the subjects achieved PASI 90 at Week 16 in the FUMADERM® arm in the BRIDGE trial.

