## **10.2 Primary Efficacy Analysis**

The primary efficacy endpoint is the proportion of subjects with a  $\geq 90\%$  reduction from baseline in Psoriasis Area and Severity Index (PASI 90) at Week 24.

The primary null hypothesis is that risankizumab is not different from FUMADERM® in achieving  $\geq 90\%$  reduction from baseline in the Psoriasis Area and Severity Index score (PASI 90) at Week 24.

The primary endpoint will be analyzed in the ITT Population. The difference in proportion of subjects achieving PASI 90 between treatment arms will be estimated and tested using the two-sided Cochran-Mantel-Haenszel risk difference estimate stratified by prior phototherapy exposure at level of significance 5%.

Non-responder imputation will be used as the primary approach for missing values. LOCF and MI will be performed as sensitivity analyses.

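### Is the stated 94% power wrong for a two-sided chi-squared test with 55 subjects per arm at 70% versus 35%?

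*Protocol*

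**What the plan says.** Protocol section 8.2 gives the whole calculation in one sentence. The test, level, sample size and power are: "Using a two-sided Chi squared test at level of significance 5%, the sample size of 110 (2 × 55) subjects will provide 94% power". The effect is fixed by "assuming response rates of the primary endpoint (PASI90 at Week 24) of 70% for risankizumab and 35% for FUMADERM". SAP section 4.3 carries the same statement: "the sample size of 110 (2 × 55) subjects will provide 94% power". Neither place says whether the chi-squared statistic is taken with or without a continuity correction.

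Three other provisions matter here.

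- **Allocation.** Under Protocol section 8.3, subjects are "randomized in a 1:1 ratio to receive risankizumab or FUMADERM® stratified by prior phototherapy", so the two arms are equal in size by design.
- **Missing data.** Under Protocol section 8.1.4, "a subject with missing PASI90 at Week 24 will be considered a non-responder in the primary analysis". Dropout is absorbed into the response rates, and section 8.2 states no separate inflation of the sample size.
- **Primary test.** Protocol section 8.1.4 says that the primary endpoint "will be analyzed using a two-sided Cochran-Mantel Haenszel test stratified by prior phototherapy at level of significance 5" per cent. SAP section 10.2 says that the difference will be "estimated and tested using the two-sided Cochran-Mantel-Haenszel risk difference estimate stratified by prior phototherapy exposure at level of significance 5" per cent. SAP section 10.1.1 gives the formulas: a weighted risk difference divided by its standard error and referred to the normal distribution. The only adjustment is 0.1 added to the cells of a stratum that contains a zero.

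**The concern.** A statistician checking section 8.2 would normally start with the uncorrected pooled-variance formula, which gives between 96% and 97%, not 94%. No uncorrected approximation that was tried comes down to 94%; they run from 95.7% to 97.5%. The stated figure then seems to belong to some other procedure, such as Fisher's exact test, which is not the primary analysis.

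This sentence is the only quantitative justification of the sample size, and it stands in both documents. If it were wrong, the type II error would be misreported: 6% stated, against 3.4% by the uncorrected formula or 3.8% by exact enumeration. It could also be said that fewer subjects would do, because the uncorrected formula reaches 94% with 48 per arm. Protocol section 5.1 says that the trial should not enrol more subjects than its objectives need, so that comparison would carry some weight.

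**Working it through.** **Inputs** (Protocol 8.2, repeated in SAP 4.3): n = 55 per arm, p1 = 0.70, p2 = 0.35, two-sided level 0.05, so z = 1.96. The difference is 0.35 and the average rate is (0.70 + 0.35)/2 = 0.525.

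**Step 1: the stated figure, with continuity correction.** The corrected test rejects when (|difference in observed proportions| − 1/55) divided by the pooled standard error is at least 1.96. Power is the sum of the binomial probabilities of all pairs of responder counts that meet this condition. Result: 0.9417, or **94.2%**, which rounds to the stated 94%. Fisher's exact test, enumerated in the same way, also gives 0.9417.

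**Step 2: the same correction by normal approximation.**
- Standard error under the null: √(2 × 0.525 × 0.475 / 55) = 0.0952
- Standard error under the alternative: √((0.70 × 0.30 + 0.35 × 0.65) / 55) = √(0.4375 / 55) = 0.0892
- (0.35 − 1/55 − 1.96 × 0.0952) / 0.0892 = 1.63, so power is 0.948

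This approximation rounds to 95%, so the closest match to the documents is the exact figure in Step 1. The corrected sample-size formula points the same way: 54 per arm for 94% and 56 for 95%, with the planned 55 in between.

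**Step 3: without correction.**
- Formula: (0.35 − 1.96 × 0.0952) / 0.0892 = 1.83, so power is 0.9665 (**96.6%**)
- Exact enumeration of the Pearson test: 0.9616 (**96.2%**)
- Sample size for 94%: 48 per arm (94.2%; 47 per arm gives 93.8%)

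**Step 4: the planned primary analysis.** This was simulated with 200,000 runs. The assumptions are the same response rates in both strata and prior phototherapy in about 10% or 20% of subjects (5 or 11 per arm; section 8.3 caps the share at 20%).

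| Analysis | Power |
|---|---|
| SAP 10.1.1 weighted risk difference | about 96.9% |
| Classical Cochran-Mantel-Haenszel, uncorrected | about 96.2% |
| Classical Cochran-Mantel-Haenszel, continuity-corrected | about 94.2% |

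These runs omit the SAP's 0.1 adjustment for zero cells. A repeat with the adjustment gave practically the same power.

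**Step 5: comparison.** The stated 94% agrees with the corrected test to rounding. Against the uncorrected test it is low by 96.2 − 94 = 2.2 points (exact) or 96.6 − 94 = 2.6 points (formula). Against the SAP's own statistic it is low by 96.9 − 94 = 2.9 points.

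**The case for a change.** The best argument for a correction is that a power statement should describe either the test as written or the test that will be run. An unqualified chi-squared test is usually read as the uncorrected one, and the primary analysis has no continuity correction. On that reading 94% describes neither, and a reader cannot tell whether the gap is an error, a hidden allowance or a different method.

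Part of this stands. The documents do leave the convention unstated, and the figure is not the power of the primary analysis. But section 8.2 does not claim that it is: it openly names a simple unstratified test, while section 8.1.4 names a stratified one. Sizing a stratified comparison of proportions with a simple two-sample test is common practice. A continuity-corrected chi-squared test is still a chi-squared test, so the label is not false.

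The comparison with 48 per arm does not stand. It holds only for the uncorrected formula. The documents do not say that the sample size was solved for a 94% target; they report the power that 110 subjects give. Nor are corrected or exact methods foreign to the plan. Fisher's exact test is used for adverse events (Protocol 8.1.5, SAP 11.1) and, where appropriate, for baseline variables (Protocol 8.1.3, SAP 7.1), although not for efficacy.

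**Conclusion.** The concern does not hold. With every stated input unchanged, a standard version of the named test gives 94.2%, so the reported 94% is reproducible. What remains is one unstated detail, the continuity correction. That the sponsor used it is an inference from the match, since the documents do not say so. Its effect is to understate the power of the uncorrected analysis by about 2 to 3 points. A trial that promises 94% and has 96% to 97% under its own assumptions is not undersized, and no estimate, significance level, test or decision depends on the difference. Replacing 94% by about 96% would only exchange one defensible approximation for another.

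This rests on the documents' assumed rates of 70% and 35%, on 55 subjects per arm with missing outcomes counted as non-response within those rates, and, for the stratified figures, on equal rates across the phototherapy strata. Whether 70% and 35% are well chosen is a separate question, not examined here.

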## **8.3 Randomization Methods**

An IVR/IWR system will be used to determine the randomization of subjects. Detailed instructions for using the IVR/IWR system will be provided to the site personnel.

The randomization schedule will be prepared by the statistics department of AbbVie. Subjects who are eligible based on inclusion and exclusion criteria and have had all pre-randomization procedures performed will be randomized in a 1:1 ratio to receive risankizumab or FUMADERM® stratified by prior phototherapy, with a maximum of 20% of subjects with prior phototherapy. Randomization will not be stratified by center due to the limited number of subjects per center. Randomization will be done using an adequate block size.

